1.1.3.5 Population Pharmacokinetic and Pharmacodynamic (PKPD) Modeling

A population pharmacokinetic model of lurtinectedin was developed by pooling data from all studies (including drug combination studies) and it is regularly updated.

A population pharmacokinetic three-compartment model with linear elimination and linear distribution adequately fits the PK data. The model estimated a mean (standard deviation [SDev]) CL of 12.3 (7.0) L/h, a half-life (HL) of 47.2 (31.5) hours and a wide volume of distribution at steady state (V_{ss}) of 436 (250) L. All these PK parameters showed high variability (coefficient of variation [CV] about 50%) among patients. The lurtinectedin PK showed linearity among the dose range explored (0.5-4.5 mg/m²).

Baseline covariates affecting lorbinecetin CL are albumin, alpha 1-acid glycoprotein, BSA, the presence of strong (voriconazole) or moderate (aprepitant or fluconazole) CYP3A4 inhibitors, and cardiac function measured by left ventricular ejection fraction (LVEF). The use of strong (voriconazole) or moderate (fluconazole or aprepitant) CYP3A4 inhibitors reduced lorbinecetin CL by approximately 40% and 20%, respectively. Therefore, the use of CYP3A4 inhibitors should be carefully monitored or avoided, whenever possible.

Renal elimination of lorbinecetin was minor in the FiH trial. In addition, the population PK model did not establish any relationship between lorbinecetin CL and CLcr or creatinine levels. Age and race were found to have no effect over lorbinecetin PK, although the number of elderly patients (>75 years) and non-Caucasian patients was small.

Lorbinecetin-induced neutropenia and thrombocytopenia population PKPD models showed that baseline ANC and platelet count are by far the covariates with the greatest effect on the incidence of neutropenia and thrombocytopenia. With a baseline absolute neutrophil count (ANC) value of $2.0 \times 10^9/L$ (currently the lower limit of ANC for inclusion is $1.5 \times 10^9/L$), and a platelet count of 135×10^9 (currently the lower limit of platelet count for inclusion is $100 \times 10^9/L$), the incidence of grade 3/4 neutropenia and thrombocytopenia were estimated to be around 69% and 13%, respectively, in the first cycle. Simulations performed at 3.2 mg/m^2 showed a lower neutropenia and thrombocytopenia incidence compared to the previous RD of 7.0 mg FD . The results of the simulation also showed that BSA-dosing reduced the variability caused by BSA compared to 5.7 mg FD . The presence of ascites or the use of CYP3A4 inhibitors would increase the incidence of neutropenia, while the use of granulocyte colony-stimulating factor (G-CSF) would decrease it markedly. Additionally, breast cancer patients showed less risk of developing thrombocytopenia, while the use of strong CYP3A4 inhibitors, ascites or pancreatic cancer increased this risk. The population PK model of lorbinecetin showed that CL increases with BSA, and the population PKPD models for neutropenia and thrombocytopenia showed myelosuppression would be decreased by BSA dosing. Therefore, the use of a BSA-dosing strategy for lorbinecetin has been resumed in ongoing and planned trials.

1.2 OVERALL STUDY RATIONALE

Lorbinecetin is extensively metabolized by the cytochrome P450 enzymes, primarily CYP3A4. Thus, potent inducers or inhibitors of this enzyme may alter the plasma concentrations of lorbinecetin. This study is designed to examine the PK and safety of lorbinecetin when co-administered with bosentan, a moderate CYP3A4 inducer, in comparison with lorbinecetin alone. The results of this study may be used to support future clinical studies in patients and prescribing information in future labeling.

1.3 PHARMACOGENETIC SUB-STUDY RATIONALE

Germline genetic variants may influence exposure and toxicity (i.e. disposition, metabolism and safety) to lorbinecetin. In order to explore the potential impact of genetic factors that may account for inter individual variability in the main PK parameters, blood sample for germline DNA extraction will be collected and stored for future pharmacogenetic (PGt) analysis. One blood sample obtained at any time during the study, but preferably just before infusion start in Cycle PK sample #1 on Day 1 of Cycle 1 will be obtained.

2. STUDY OBJECTIVES

2.1 PRIMARY OBJECTIVE

- To assess the effect of bosentan on lorbinecetin total plasma exposure in patients with advanced solid tumors.

2.2 SECONDARY OBJECTIVES

- To assess the effect of bosentan on lorbinecetin unbound plasma exposure.
- To assess the effect of bosentan on lorbinecetin major metabolites (i.e., M1 and M4).
- To assess the effect of bosentan on the safety profile of lorbinecetin.
- To collect and store a blood sample for germline DNA extraction for future pharmacogenetic (PGt) analysis of variations on genes that may influence exposure and response (i.e., disposition, metabolism and safety) to lorbinecetin.

3. OVERALL STUDY DESIGN

3.1 STUDY DESIGN

This is a prospective, open-label, two-way crossover, phase Ib drug-drug interaction study in patients with advanced solid tumors.

The study will include a pre-treatment (screening) phase followed by a treatment phase consisting of two lorbinecetin cycles, one cycle in combination with bosentan and one cycle of lorbinecetin as single agent (in different order depending on the study sequence), and one additional third cycle of lorbinecetin as a single agent for patients who meet the continuation criteria and obtain a clinical benefit after the first two cycles, and then follow-up of adverse events if any.

Patients who meet the continuation criteria and obtain a clinical benefit after the first two cycles according to the Investigator's criteria will have the opportunity to continue treatment under a Compassionate Use Agreement after the completion of the optional third study cycle.

Patients will be treated as outpatients. At the discretion of the Investigator, patients may be admitted to the study center on Day -1 or Day 1 and monitored, at least, until completion of the Day 1 PK blood sample collections.

Patients will receive a maximum of three cycles: two consecutive cycles of lorbinecetin, one cycle with and one cycle without bosentan co-administration (in different order depending on the study Sequence 1 or Sequence 2 of treatment), followed by a third cycle with lorbinecetin alone (this last optional for patients with clinical benefit). Lorbinecetin will be administered as a 1-hour (-5/+20 min) i.v. infusion q3wk via a central or peripheral vein.

[figure not shown]
In the co-administration cycles, bosentan will be administered orally twice daily in the morning and evening during the prior five consecutive days, self-administered at home from Day -5 to Day -1 (i.e., five days before lorbinecetin infusion), and once daily on

Day 1 (i.e., the day of lorbrena infusion), following recommendations at the Summary of Product Characteristics (SmPC). On Day 1 (i.e., the day of lorbrena infusion), bosentan will be given immediately prior to starting the lorbrena infusion. In fact, bosentan should be administered after obtaining the bosentan pharmacokinetic (PK) sample #1 and before the start of lorbrena infusion (-15 min to -1 min).

In case of lorbrena delay (≤ 2 days), bosentan could be administered twice daily during a maximum of seven consecutive days before lorbrena infusion, and supplied at the study center once daily on Day 1 (before lorbrena infusion).

All patients will receive a maximum of three cycles: two consecutive cycles of lorbrena, one cycle with and one cycle without bosentan co-administration (in different order depending on the study Sequence 1 or Sequence 2 of treatment), followed by a third cycle with lorbrena alone (this last optional for patients with clinical benefit). Patients will be randomized in a 1:1 ratio ([Figure 2](#)) to Sequence 1 (TR: Test- Reference; lorbrena + bosentan in Cycle 1) or Sequence 2 (RT: Reference-Test; lorbrena + bosentan in Cycle 2). Lorbrena will be administered as a 1-hour (-5/+20 min) intravenous (i.v.) infusion every three weeks (q3wk) via a central or peripheral vein. The dose of lorbrena will be 3.2 mg/m² for all patients when administered with and without bosentan. If toxicity occurs, the appropriate intra-patient dose level (DL) reductions will be implemented in the subsequent cycle. This DL reduction will be according to [Table 8](#).

Figure 2. Study design.

BOS, bosentan; LRB, lorbrena; TR, test-reference; R; randomized; RT, reference-test.

The enrollment of the patients will be simultaneous. However, if once the first three patients enrolled have completed Cycle 1 and Cycle 2, total lorbrena exposure does not allow an adequate PK assessment and if no unacceptable or life-threatening toxicities have occurred, the dose of lorbrena to be co-administered with bosentan in the remaining five patients can be adjusted accordingly.

This decision will be made by the Sponsor and the study Investigators. Therefore, the planned dose of lorbrena, when given with bosentan for the remaining five patients, will be based on the acceptability of the PK and safety results from the first three patients. If the initial three patients do not experience adverse events (AEs) which might require a dose-reduction, the dose of lorbrena may still be adjusted (based on the assumption of dose-proportional pharmacokinetics) to produce plasma lorbrena area under the curve (AUC) values that are comparable to those when lorbrena is given in the absence of bosentan. However, if toxicity occurs in the initial three patients, the appropriate dose-reduction of lorbrena will be implemented in the remaining five patients accordingly.

Patients will receive lorbinecetin until disease progression, unacceptable toxicity, consent withdrawal or while it is considered to be in their best interest, and for a maximum of three cycles. Treatment with lorbinecetin outside this study could be continued under a Compassionate Use Agreement after the completion of the optional third study cycle.

All patients will be randomly assigned to the corresponding sequences:

- Sequence 1 (TR):
 - Cycle 1: Bosentan + lorbinecetin
 - Cycle 2: Lorbinecetin alone
 - Cycle 3: Lorbinecetin alone (optional)
- Sequence 2 (RT):
 - Cycle 1: Lorbinecetin alone
 - Cycle 2: Bosentan + lorbinecetin
 - Cycle 3: Lorbinecetin alone (optional)

Lorbinecetin will be administered to eight evaluable patients and for a maximum of three cycles, while considered to be on the patient's best interest or until PD, unacceptable toxicity, intercurrent illness of sufficient magnitude to preclude safe continuation of the study, patient's refusal and/or non-compliance with study requirements, a protocol deviation with an effect on the risk/benefit ratio of the clinical study, more than two lorbinecetin dose reduction due to AEs related to lorbinecetin (unless clear clinical benefit has been documented and always with the Sponsor's agreement), or any other reason at the physician's judgment that precludes lorbinecetin continuation.

If the patient meets the continuation criteria and shows a clear clinical benefit after the first two cycles according to Investigator criteria, treatment with lorbinecetin may continue outside this study under a Compassionate Use Agreement at the same dose based on Investigator's decision and upon agreement with the Sponsor. Then, the treating center must request authorization to the relevant Health Authorities and notify the Sponsor in due time. In order to avoid a treatment discontinuation, during the Compassionate Use Agreement authorization an additional third cycle with lorbinecetin is allowed.

All adverse events (AEs) will be graded according to the National Cancer Institute Common Terminology Criteria for Adverse Events (NCI-CTCAE) v.5. Treatment delays, dose reduction requirements and reasons for treatment discontinuation will be monitored throughout the study. The safety profile of patients will be monitored throughout the treatment and up to 31 days (± 10 days) after the last lorbinecetin infusion (end of treatment, EOT), until the patient starts a new antitumor therapy or until the date of death, whichever occurs first. Any treatment-emergent AEs will be followed until recovery to at least grade 1 or stabilization of symptoms or until the start of a new antitumor therapy, until the continuation of treatment outside this study under a Compassionate Use Agreement or death, whichever occurs first. After treatment discontinuation, patients will be followed until resolution or stabilization of all toxicities, if any.

Patients will be evaluated at scheduled visits on three study periods: pre-treatment (screening), treatment (one cycle of lorbinecetin in combination with bosentan and two

as a single agent and the third cycle optional) and follow-up of adverse events if any (see Section [Schedule of Assessments and Procedures](#)).

The PK (and safety) of bosentan will be assessed in the first three patients in order to confirm the above statements.

Patients will receive i.v. corticosteroids (according to institutional standard antiemetic doses, minimum dose of 8 mg/day and maximum dose of 20 mg/day of dexamethasone sodium phosphate or equivalent) 30 ± 5 minutes before the infusion of lurbinectedin during Cycles 1 and 2. The optional treatment with additional antiemetic drugs on Day 1 of Cycles 1 and 2 is allowed, but should be identical across Cycle 1 and 2 for a given patient when possible to minimize intra-subject variability in the PK of lurbinectedin. Ondansetron is the recommended serotonin (5-HT₃) antagonist, since it is metabolized by multiple hepatic cytochrome P450 enzymes. Its metabolic clearance is less likely to

be influenced by the co-administration of bosentan, relative to a serotonin receptor antagonist that is predominately metabolized by a single cytochrome P450 enzyme.

A 168-hour blood sample collection period is sufficient to assess the potential effects of bosentan on lorbinecetin systemic exposure. In order to confirm the presence of measurable bosentan exposure and provide an abbreviated profile of plasma concentrations of bosentan, four samples will be collected in the cycle during which patients receive bosentan, as detailed in the [Schedule of Assessments and Procedures section](#).

3.3 PRIMARY ENDPOINT

3.3.1 Plasma exposure to lorbinecetin

Plasma dose-normalized C_{max} and $AUC_{0-\infty}$ of lorbinecetin will be compared between Cycle 1 and Cycle 2. Pharmacokinetic analyses will be evaluated in plasma by standard non-compartmental methods, or population methods, if necessary.

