EXPECTED NUMBER OF PATIENTS	Eight patients will be enrolled. Additional patient(s) may be enrolled if any patient(s) does not complete the required assessments, including the PK blood sample collections of the first and second cycles.
REPLACEMENT OF PATIENTS	
Patients must be replaced if they are not evaluable for the assessment of the primary endpoint (e.g., if they have not sufficient and interpretable PK parameters).
 
All replaced patients who received the study treatment will be included in the general safety analysis.

STUDY DRUGS FORMULATION	
Bosentan: Commercially available bosentan film-coated tablets (with strengths of 125 mg) will be provided by the Sponsor.
 
Lurbinectedin: Lurbinectedin 4 mg drug product (DP) is presented as a lyophilized powder for concentrate for solution for infusion in 30 mL vials and will be supplied by the Sponsor for the purposes of this study. Before use, the 4 mg DP should be reconstituted with 8 mL of water for injection to give a solution containing 0.5 mg/mL of lurbinectedin. For administration to patients as an i.v. infusion, reconstituted vials are diluted with glucose 50 mg/mL (5%) solution for infusion or sodium chloride 9 mg/mL (0.9%) solution for infusion. The full composition of the lurbinectedin 4 mg DP and the reconstituted solution per mL is shown in Table S1.
 
Table S1. Composition of lurbinectedin (PM01183) vials.
 
  
 Component	Concentration/vial	Concentration/vial after reconstitution	
   
 Lurbinectedin	4.0 mg	0.5 mg/mL	
 
 Sucrose	800 mg	100 mg/mL	
 
 Lactic acid	22.08 mg	2.76 mg/mL	
 
 Sodium hydroxide	5.12 mg	0.64 mg/mL	
  
	Component	Concentration/vial	Concentration/vial after reconstitution	Lurbinectedin	4.0 mg	0.5 mg/mL	Sucrose	800 mg	100 mg/mL	Lactic acid	22.08 mg	2.76 mg/mL	Sodium hydroxide	5.12 mg	0.64 mg/mL
Component	Concentration/vial	Concentration/vial after reconstitution														
Lurbinectedin	4.0 mg	0.5 mg/mL														
Sucrose	800 mg	100 mg/mL														
Lactic acid	22.08 mg	2.76 mg/mL														
Sodium hydroxide	5.12 mg	0.64 mg/mL														

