3.4 SECONDARY ENDPOINTS

3.4.1 Secondary PK parameters

- Differences in dose-normalized total AUC_{0-t} and C_{max} and in Cl , V_{ss} and $T_{1/2}$ of lorbinecetin between Cycle 1 and Cycle 2 will be explored.
- Differences in dose-normalized unbound $AUC_{u,0-\infty}$, $AUC_{u,0-t}$ and $C_{u,max}$ and in CL_u , $V_{ss,u}$ and $T_{1/2,u}$ of lorbinecetin between Cycle 1 and Cycle 2 will be explored.
- Differences in ratios between total $AUC_{0-\infty}$, AUC_{0-t} and C_{max} , of main lorbinecetin metabolites relative to parent drug between Cycle 1 and Cycle 2 will be explored. Additional PK parameters will be calculated if deemed appropriate.

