5. PLAN OF THE STUDY

5.1 PLANNED STUDY PERIODS (FOR THE WHOLE STUDY)

The total duration of the study will be approximately 22 months, including approximately an 18-month enrollment period.

- **Planned start date** (first patient on study): 4Q2020.
- **Planned enrollment period**: approximately 18 months.
- **Planned end-of-study date** (clinical cutoff): 31 (± 10) days after the date of the last lorbinectedin administration for last patient /last cycle, or when confirmation of evaluability of at least eight patients, whichever occurs last.

Patients who meet the continuation criteria and obtain a clear clinical benefit with lorbinectedin after the completion of the first two study cycles, according to the Investigator's criteria may continue treatment outside this study under a Compassionate Use Agreement after the completion of the optional third study cycle. Should the patient continue under a Compassionate Use Agreement, the treating center must request authorization to the relevant Health Authorities and notify the Sponsor in due time.

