5.3 REPLACEMENT OF PATIENTS

Patients must be replaced if they are not evaluable for the assessment of the primary endpoint (e.g., if they have not sufficient and interpretable PK parameters).

Evaluable patients for the main objective of the study (e.g., assessment of lurbinectedin PK) should have provided sufficient and interpretable PK parameters (e.g., AUC_{0-t} should cover at least 80% of $AUC_{0-\infty}$) of Cycle 1 and 2. Evaluable patients should have received the first two complete cycles regardless dose delays or reductions.

The compliance of bosentan will be confirmed based on a patient's diary, the drug accountability and the expected individual plasma concentration at the steady state.

Any replacement subject during the treatment phase will be given a new subject number and assigned to the same sequence as the not-evaluable subject being replaced. All replaced patients who received the study treatment will be included in the general safety.

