9.3.4 Pharmacokinetics

Plasma exposure to lurbinecetin

Only patients who completed the study with sufficient and interpretable PK parameters will be included in the statistical comparison of plasma exposure to lurbinecetin.

Descriptive statistics will be used to summarize pharmacokinetic data.

The primary parameter of interest for the statistical analysis will be plasma dose-adjusted $AUC_{(0-\infty)}$ (if data do not permit so, $AUC_{(0-t)}$ will be used) of lurbinecetin. The

analysis will compare the log-transformed AUC for lubrinedin administered in combination with bosentan (Test) to the lubrinedin alone (Reference).

A mixed-effects model will be fit to the data with log-transformed AUC as the dependent variable, treatment (Test or Reference), period and sequence as fixed effects, and patient (sequence) as a random effect. The estimated least square means and intrasubject variability from the mixed-effects model will be used to construct 90% CIs for the difference in means on the log scale between treatments (Test or Reference). The adjusted mean differences and the 90% CIs will be exponentiated to obtain estimates of the ratio of adjusted geometric means (Test/Reference) and 90% CIs for the ratios.

A large difference (e.g. two-fold difference shown from CIs and least square means) will be considered to show evidence on whether bosentan co-administration has a clinically relevant effect on lubrinedin exposure.

Secondary PK parameters

Similar models used for the primary endpoint will be fit to the data with dose-normalized $AUC_{(0-t)}$ and C_{max} and in C_l , V_{ss} and $T_{1/2}$ of lubrinedin or metabolite to parent exposure PK parameters ratio, as the dependent variable. Results will also be assessed graphically.

Plasma protein binding

A similar model used for the primary endpoint will be fit to the data with dose-normalized AUC_u as the dependent variable.

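### Does listing Cmax as both a primary and a secondary endpoint leave it open which patients must be replaced?

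*Protocol*

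**What the plan says.** **Endpoint lists.** Protocol 3.3.1, the synopsis and SAP 4.2.1 name dose-normalized Cmax and AUC0-∞ together as the primary endpoint, which "will be compared between Cycle 1 and Cycle 2. Pharmacokinetic analyses will be evaluated in plasma by standard non-compartmental methods". Protocol 3.4.1, the synopsis and SAP 4.2.2 then list Cmax among the secondary parameters, in the item that begins "Differences in dose-normalized total" AUC0-t.

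**Analysis.** Protocol 9.3.4 is narrower. "The primary parameter of interest for the statistical analysis will be plasma dose-adjusted" AUC0-∞, with AUC0-t as fallback. Cmax comes under the secondary PK parameters: "Similar models used for the primary endpoint will be fit to the data with dose-normalized" AUC0-t and Cmax, among others.

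**Replacement.** Protocol 5.3 and SAP 5.1 say: "Patients must be replaced if they are not evaluable for the assessment of the primary endpoint". Both explain this by the example of a patient whose PK parameters are too few or not interpretable. The one numerical criterion, also introduced as an example, is that AUC0-t "should cover at least 80% of" AUC0-∞. The synopsis (Expected number of patients) adds: "Additional patient(s) may be enrolled if any patient(s) does not complete the required assessments", and counts the PK samples of the first two cycles among those assessments. By protocol 5.1, the study ends 31 (±10) days after the last lurbinectedin administration "or when confirmation of evaluability of at least eight patients, whichever occurs last".

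**Deferral.** SAP section 6 leaves the PK definitions and PK analysis plan to a separate Clinical Pharmacology document, which is not among the documents reviewed.

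**The concern.** Taken literally, two routes through the text give opposite actions for the same patient. If Cmax is part of the primary endpoint (3.3.1), a patient without a usable Cmax is not evaluable for all of it and must be replaced. If AUC alone is primary (9.3.4), the patient stays. The case can be imagined: Cmax is the highest observed concentration (8.1.3), only sample #2 is drawn close to the end of infusion (Table 9), and the SAP plans a listing of interrupted lurbinectedin infusions.

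With a target of eight evaluable patients, the choice would decide who enters the primary comparison. It would also decide whether one more patient receives a genotoxic drug and bosentan. The trial is open-label and PK is reviewed after the first three patients, so an unsettled rule could be settled after concentrations are known.

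The endpoint wording also speaks of Cycle 1 against Cycle 2, although the question is Test against Reference. In a crossover, a literal comparison of cycles estimates a period effect.

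**Working it through.** **1. What decides evaluability.**

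| Place | Test applied | Does it use the primary/secondary label? |
|---|---|---|
| Protocol 5.3, SAP 5.1 (replacement) | Evaluable for the primary endpoint, explained as having adequate, interpretable PK parameters | Named, then explained without it |
| Synopsis, Evaluability; protocol 5.3 | Adequate, interpretable PK parameters in Cycles 1 and 2; both cycles received | No |
| Protocol 9.1, 9.3.4; SAP 3 (analysis set) | The same phrase | No |
| Synopsis, Expected number of patients | Required assessments complete, including PK samples | No |

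The working test is the same throughout and concerns the quality of the PK profile. Moving Cmax from one list to the other leaves it unchanged. That a patient must be replaced under 3.3.1 but not under 9.3.4 is an inference; neither section says so.

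**2. The plan's own precision figure.** Inputs from protocol 9.2 and SAP 5.2: eight patients, 1:1, intra-subject CV 40%. With the CV used as the log-scale SD:

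half-width = t(0.95, n−2) × σ × √[(1/n₁ + 1/n₂)/2]

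- 4 + 4 patients: 1.943 × 0.40 × √[(1/4 + 1/4)/2] = 1.943 × 0.40 × 0.500 = 0.389, as stated.
- Back-transformed at ratio 1: exp(−0.389) = 0.678 and exp(0.389) = 1.475. The upper limit agrees with the stated 147%; the lower rounds to 68%, not the stated 70%. That is a separate matter and has no bearing here.
- If one patient lacked a Cmax and was not replaced (4 + 3): 2.015 × 0.40 × √[(1/4 + 1/3)/2] = 2.015 × 0.40 × 0.540 = 0.435 for Cmax. AUC stays at eight patients and 0.389.

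**3. Effect of exchanging one patient.** The SD of a within-patient log difference is √2 × 0.40 = 0.566. At 4:4 each patient has weight 1/8 in the treatment contrast. Replacing one patient by another gives SD = √2 × 0.566 / 8 = 0.80 / 8 = 0.10, about 10% on the ratio scale. This is about a quarter of the half-width (0.10 / 0.389 = 0.26), and it has no direction as long as the exchange does not depend on the observed ratio.

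**4. Can Cmax be lost while AUC is sound?** The documents do not give the central volume, so this is an illustration only. It uses a two-compartment curve with CL 12.3 L/h, half-life 47.2 h and Vss 436 L (protocol 1.1.3.5), an assumed central volume of 15 to 150 L, and the protocol's sampling times and linear-log rule. Results are relative to a complete 1-hour infusion profile.

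| Central volume (L) | Sample #2 missing: Cmax ratio | Sample #2 missing: AUC0-∞ ratio | Sample #2 missing: AUC0-t/AUC0-∞ | 30-min interruption: Cmax ratio |
|---|---|---|---|---|
| 15 | 0.46 | 0.79 | 0.942 | 0.80 |
| 25 | 0.65 | 0.87 | 0.949 | 0.83 |
| 50 | 0.85 | 0.94 | 0.956 | 0.90 |
| 100 | 0.97 | 0.97 | 0.960 | 0.95 |
| 150 | 1.00 | 0.98 | 0.962 | 0.97 |

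With sample #2 missing, Cmax and AUC deteriorate together. Where Cmax is badly lost, AUC is damaged as well; where AUC is intact, so is Cmax. An interruption leaves AUC0-∞ within about 1% and lowers Cmax by 3 to 20%, but the value is still observed and nothing in the documents declares it invalid. The infusion window already allows up to 80 minutes (1 hour, −5/+20 min), which in the same curve lowers Cmax by 1 to 16%.

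**5. Cycle wording.** Section 9.3.4 fits treatment, period and sequence and estimates Test/Reference. That fixes the comparison whatever the endpoint sentence says.

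**The case for a change.** The strongest reply is that the replacement rule sits in the protocol and in SAP 5.1, which sites and the randomization system follow, and that a separate PK plan may not reach them in time. The 80% criterion is only an example and concerns AUC, so it does not say whether Cmax is needed. In an open-label trial with an early look at PK, leaving this to judgement is what prespecification is meant to avoid, and an unnecessary replacement exposes another patient.

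Part of this stands. The double listing is an error of drafting, and no section of the two documents says which parameters must be valid. But the open item is what counts as adequate and interpretable, and relabelling Cmax would not close it.

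Tying replacement to AUC alone would not clearly improve matters either. In the illustration, a profile without sample #2 passes the 80% rule with 94 to 96% coverage while its AUC0-∞ is 2 to 21% low. An AUC-only rule resting on that criterion could therefore keep a distorted profile in an eight-patient comparison. The present wording lets the pharmacokineticist look at the whole profile, and the synopsis already permits an added patient when samples are missing. At most, the label turns that permission into an obligation.

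**Conclusion.** No change to the plan is needed. Cmax carries two labels, but nothing statistical depends on which one is right. There is no alpha split, power claim or success rule attached to it, and AUC and Cmax receive the same type of mixed model and 90% CI. Section 9.3.4 is specific enough for an analyst to take AUC0-∞ as primary and report Cmax beside it. The wording about Cycle 1 and Cycle 2 is likewise clerical, because the model estimates Test/Reference.

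The effect on replacement is narrow and inferred. It needs a profile whose AUC is sound and whose Cmax is judged unusable, and the documents define no such case. Were it to occur, exchanging one patient would move the log ratio at random with an SD of about 0.10; keeping the patient out of the Cmax model only would widen the Cmax half-width from 0.389 to 0.435.

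This rests on the documents' 40% CV, on four patients per sequence, and on evaluability being judged from sampling and infusion records rather than from the Test/Reference result. The separate Clinical Pharmacology document, not seen here, is the natural place for the definition of a valid parameter. The central volume in the illustration is an assumption, and the conclusion does not depend on it.
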